12.2 Assessment of Adverse Events

All AEs both non-serious and either temporally or causally related to study procedures will be assessed by the Investigator and documented in LORIS. Details of the event must include the dates of onset and resolution, severity, relationship to study procedures, seriousness, whether the event caused the participant to withdraw from the study, and outcome.

Severity: Severity should be graded and recorded according to the table below.

Severity	Definition
Mild	Awareness of event but easily tolerated
Moderate	Discomfort enough to cause interference with usual activity
Severe	Inability to carry out usual activity, incapacitating, requires medical intervention

Relationship: The relationship of the AE to study procedures will be determined by the Investigator, and assessed using the following definitions:

Relatedness	Description
Not Related	There is no evidence of a causal relationship and a causal relationship cannot be reasonably attributed to the study procedures. The event is clearly due to non-study causes.
Unlikely Related	A poor temporal relationship exists between the event onset and study procedures. The event could easily be explained by the participant's clinical state, intercurrent illness, or concomitant therapies.
Possibly Related	A relationship between event onset and study procedures cannot be ruled out with certainty and the event may be related. There is some evidence to suggest a causal relationship but the influence of other factors may have contributed to the event, such as the participant's clinical condition or concomitant treatment.
Probably Related	The event is likely related to study participation. There is evidence to suggest a causal relationship, such as reasonable temporal sequence from procedure. The influence of other factors is unlikely.
Definitely Related	The event is clearly related to study participation. There is clear evidence to suggest a causal relationship. The influence of other factors can be ruled out.

These criteria, in addition to good clinical judgment, should be used as a guide for determining the causal assessment.

12.3 Collection and Reporting of Serious Adverse Events (SAEs)

All SAEs thought to be **unanticipated and related to study procedures** must be collected from the time of the baseline visit and up to 30 days after study participation has ended. SAEs will be promptly assessed by the Investigator and documented in LORIS as described below.

In order to meet the requirements for reporting as an SAE in LORIS, an event **must meet all three criteria** as defined below:

- 1) **Serious**
 - a. Untoward occurrence that results in death, is a life-threatening situation, requires inpatient hospitalization or prolongation of existing hospitalization, results in significant disability/incapacity or is a congenital anomaly
- 2) **Unanticipated**
 - a. An AE that is not identified in nature, severity, or frequency in the relevant safety documents(s) or is not identified as a possible risk in the study protocol or the informed consent form
- 3) **Related to study procedures** in the judgement of the Principal Investigator taking into account all aspects of the event

If the Investigator believes that an SAE is related to a study procedure, this should be specified in the narrative section of the SAE report.

SAEs meeting the above definition must be reported in LORIS **promptly, but no later than 10 business days** of the Investigator becoming aware of the event.

In addition, Investigators must report SAEs to their local IRB/REB according to local safety reporting guidelines for submission of SAEs.

SAE information including event term, start/stop dates, severity, relationship to study procedures, whether the event caused the participant to withdraw from the study, and outcome will be entered into LORIS as specified in the Study Procedures Manual.

If only limited information on the SAE is initially available, follow-up reporting is required. If an ongoing SAE changes in its intensity or relationship to study procedures or if new information becomes available, a follow-up SAE report should be entered into LORIS within 10 days of the Investigator becoming aware of the updated information using the same procedure used for the transmission of the initial SAE and the same event term should be used. All SAEs should be followed to resolution or stabilization. For any questions relating to SAEs, please contact the CCNA coordinating center via telephone or email at the number listed in the Study Procedures Manual.

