12.0 ADVERSE EVENTS

An adverse event (AE) is any untoward medical occurrence in a participant that occurs from the time of the baseline visit and up to 30 days after study participation has ended. For the purposes of reporting on the CTU study, an AE is defined as any unfavourable or unintended sign (e.g., including an abnormal laboratory finding), symptom, or disease associated with study procedures that are both **non-serious and either temporally or causally related to study procedures**. Pre-existing conditions, which increase in frequency or severity or worsen in nature during, or as a consequence of, a study procedure, may also be considered an AE if it meets the definition of being both non-serious and related to a study procedure.

An AE **does not** include:

- Medical or surgical procedures (e.g., surgery, endoscopy, tooth extraction, transfusion). The condition that leads to the procedure is the AE.
- Situations where an untoward medical occurrence has not occurred (e.g., hospitalization for elective surgery, social and/or convenience admissions).
- Worsening of symptoms associated with expected decline in memory or an associated co-morbid condition and not related to a study procedure.
- Those medical or surgical adverse events that are not related to the study procedures

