12.1 Evaluation and Reporting of Adverse Events

All AEs both non-serious and either temporally or causally related to study procedures (i.e., a new event or an exacerbation of a pre-existing condition) that occur from the baseline visit and up to 30 days after study participation has ended will be recorded as an AE in LORIS. Adverse events that occur prior to the baseline visit will be documented as medical history. The Investigator must follow all AEs until the AE resolves, or until the Investigator determines the event is chronic or clinically stable. If an AE remains unresolved at the conclusion of participation in the BHSP, the Investigator will make a clinical assessment to determine whether continued follow-up of the AE is warranted.

The Investigator should attempt to establish a diagnosis of the event based on signs, symptoms and/or other clinical information. In such cases, the diagnosis should be documented as the AE and not the individual signs/symptoms.

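### A serious, procedure-related event judged anticipated enters neither LORIS safety log; Protocol 12.0 to 12.3 should be reconciled

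*Protocol*

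**What the plan says.** **AE record.** Protocol 12.0 gives a general definition of an adverse event and then narrows it, for study reporting, to events that are "non-serious and either temporally or causally related to study procedures". Sections 12.1 and 12.2 repeat the limit for what is recorded and assessed in LORIS: "All AEs both non-serious and either temporally or causally related to study procedures". Section 12.0 also lists what is not an AE, including "Those medical or surgical adverse events that are not related to the study procedures".

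**SAE record.** For LORIS entry as an SAE, Protocol 12.3 says an event "must meet all three criteria": serious, unanticipated, and related to study procedures. Its opening sentence applies the last two conditions to the collection of SAEs as well as to their reporting. Relatedness is decided "in the judgement of the Principal Investigator taking into account all aspects of the event". An event is unanticipated if it is "An AE that is not identified in nature, severity, or frequency in the relevant safety documents(s"), or if it is not named as a possible risk in the protocol or consent form. Qualifying SAEs go into LORIS within 10 business days.

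**Other routes.** SAEs go to the local ethics board under local rules (Protocol 5.2 and 12.3). Changes in medical history are reviewed at Month 6 and documented at Month 12 (8.1.6 and 8.1.8). The SAP has no safety section.

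**The concern.** The two rules are meant to divide the procedure-related events between two logs, but they do not meet. The AE rule closes at seriousness. The SAE rule then adds a second condition, that the event be unanticipated, which the AE rule does not have. A serious, related event judged anticipated falls between them.

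A second gap may exist. A link in time is enough for an AE. Section 12.3 says only *related*, without stating whether a link in time counts. If it does not, a non-serious event linked only in time is logged and a serious one is not.

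The filter on serious events is therefore tighter than the filter on non-serious ones. Anticipation normally sets how fast an event is reported; here it also decides whether a safety record exists. Any safety summary drawn from the two logs would omit such an event without showing that it had done so.

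**Working it through.** No figure is at issue, so the check is to list the possible kinds of event and apply both rules to each. Seriousness has 2 levels, anticipation 2, and the link to procedures 3 (causal, time only, none), which gives 2 × 2 × 3 = 12 combinations.

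- AE rule (12.0 to 12.2): non-serious, with a causal or time link.
- SAE rule (12.3): serious, unanticipated and related.

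| Serious | Anticipated | Link to procedures | Combinations | AE log | SAE log |
|---|---|---|---|---|---|
| No | Either | Causal | 2 | Yes | No |
| No | Either | Time only | 2 | Yes | No |
| No | Either | None | 2 | No | No |
| Yes | No | Causal | 1 | No | Yes |
| Yes | Yes | Causal | 1 | No | **No** |
| Yes | No | Time only | 1 | No | Depends on *related* |
| Yes | Yes | Time only | 1 | No | **No** |
| Yes | Either | None | 2 | No | No |

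**Count.** The AE log takes 2 + 2 = 4. If *related* in 12.3 means causal, the SAE log takes 1, and 12 − 4 − 1 = 7 enter neither log. If a link in time also counts, the SAE log takes 2, and 12 − 4 − 2 = 6 enter neither.

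**Which of these matter.** Four of the unlogged combinations have no link to procedures (2 non-serious, 2 serious). Both rules leave those out alike, and they are not the point here. Among linked events, all 4 non-serious combinations are logged, against 1 of 4 serious ones (causal reading) or 2 of 4 (broader reading). On either reading the serious, causal, anticipated combination is unlogged. These are counts of kinds of event, not of expected events.

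**How often it could occur.** Protocol 5.5.1 lists fatigue and frustration from testing, lowered mood from questionnaires, minor discomfort or disturbed sleep from the devices, and a confidentiality breach. None is described at a level that meets the seriousness test in 12.3 (such as death, a threat to life, hospital admission or lasting disability). The definition of *unanticipated* has alternative limbs, and unlisted severity satisfies one of them. A listed risk that led to hospital admission could therefore usually be classed as unanticipated and would be logged. The consent form and the safety documents mentioned in 12.3 are not available here, so the size of the gap cannot be fixed.

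**Two related inconsistencies.** Section 12.2 asks for seriousness to be recorded for events already restricted to non-serious ones. Section 12.3 makes relatedness a condition of entry, then treats it as open: "If the Investigator believes that an SAE is related to a study procedure, this should be specified".

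**The case against.** The strongest reply is that the filter is deliberate and suits a remote educational study with minimal stated risk, and that on the protocol's own risk list the gap is close to empty. That stands as to size.

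A reader might infer that any serious event of a kind named in the protocol is shut out. The text does not support this: naming the kind of event is not enough to make it anticipated if its severity or frequency is unlisted.

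A reader might also see a contradiction in the relatedness table of 12.2, which includes a category described as "There is no evidence of a causal relationship and a causal relationship cannot be reasonably attributed to the study procedures". There is none. An event linked only in time qualifies as an AE and still needs a causality grade, which may properly be that one.

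The gap for serious events linked only in time depends on reading *related* as causal. Section 12.3 leaves the judgement to the investigator on all aspects of the event, and 12.2 treats timing as evidence, so a broader reading is open. The point is that the protocol does not say.

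The seriousness field and the conditional sentence can fairly be called loose drafting. They lose no data by themselves, but they leave the intended rule unclear.

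Other routes do exist. The medical-history updates and ethics board reports may capture such an event, and clinical data are entered in LORIS (14.1.1). However, the protocol does not describe those updates as a safety record with relatedness and outcome, and ethics reporting follows local rules.

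What the reply does not answer is why an anticipated, related event should be logged when non-serious and not logged when serious.

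**Conclusion.** The gap follows from the text: a serious, procedure-related event judged anticipated has no place in either LORIS safety log, and neither the rest of the protocol nor the SAP gives it one. The parallel gap for serious events linked only in time is conditional on a causal reading of *related* in 12.3.

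The expected number is likely to be very small. That rests on the minor risks in 5.5.1, on the severity limb of *unanticipated* being applied as written, and on the unseen consent form and safety documents not listing serious outcomes.

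Two stronger conclusions are not supported. One is that a known share of serious events will be lost: capture in this class is nil by definition, but the documents do not show that the class has any members. The other is that such events would be reported nowhere. The defect does not touch the primary analysis. It is worth correcting because the correction is cheap and the unlogged events are serious ones.

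**What to change.** Reconcile Protocol 12.0 to 12.3 as follows.

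1. Record in LORIS every serious event related to study procedures. Keep *unanticipated* as a recorded attribute that sets the reporting timeline, not as a condition of entry.
2. State whether *related* in 12.3 means the same as in 12.0 (in time or by cause), and which of the five relatedness categories in 12.2 count.
3. Either remove the seriousness field from the AE record or explain its use, and reword the conditional sentence on SAE relatedness to agree with the entry rule.

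The cost is protocol wording, one form field and a few more site entries. If serious events linked only in time are included, the entries will be more numerous: the study follows up to 350 people aged 60 to 85 for 12 months with repeated procedures, so some unrelated hospital admissions would qualify. The sponsor should weigh that when settling item 2.

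If follow-up is already complete, the sponsor can check medical-history updates and ethics submissions against the LORIS logs and state the entry rule as a limitation in the report.

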13.0 STATISTICAL CONSIDERATIONS

13.1 Sample Size and Power

With a baseline (t1) sample size of 350 participants and an anticipated 20-30% range of drop-out rates, we will have between 245 (with 30% dropout) and 280 (with 20% dropout) completed participants at t2 (end of intervention). All calculations are for 80% power and 5% two-tailed alpha. We considered small ($d=0.2$) and medium ($d=0.5$) Effect Sizes for 4 different t_1-t_2 correlations ($r_{t_1-t_2}$) in the primary outcome variable: $r=0.2, 0.3, 0.4$ and 0.5 . A final sample of $n=280$ will allow us to detect an $ES \geq 0.2$ if $r_{t_1-t_2} \geq 0.3$. A final sample of $n=245$ will allow us to detect an $ES \geq 0.2$ if $r_{t_1-t_2} \geq 0.4$ (please see Table 1 for required sample sizes, and Appendix 4 for supporting formulae).

Table 1: Required sample size to detect $ES = 0.2$ or 0.5 across a range of $r_{t_1-t_2}$ with statistical power = 0.8 and two-tailed alpha error = 0.05.

Effect Size (ES)	$r_{t_1-t_2}$	n
0.2 (small)	0.2	316
	0.3	277
	0.4	238
	0.5	198
0.5 (medium)	0.2	53
	0.3	46
	0.4	40
	0.5	34

It is estimated that approximately 50% of participants will own a smartphone with internet access appropriate for use of the MyCogHealth mobile cognitive assessment (n=175) and an additional 150 will be provided with Android devices (total approx. n = 325).

CTU will provide 120 Axivity devices and 60 EEG headbands to be used for the duration of this study, which should allow for all participants to participate in recordings at Baseline and Month 12. Devices will be centrally distributed from SRI to participants.

13.2 Analysis Plan

In our one-group pretest-posttest design the major interest is within-person change in the primary and secondary outcomes over time (response variables) in the presence of one or more explanatory variables that are categorical or continuous. The data will be analyzed using a mixed model for repeated measures approach (MMRM). This approach will treat sites and participants as random effects, while observational time and their characteristics such as sex and age as fixed effects. Potential effect modifications will be examined using this MMRM approach with variable selection based on Akaike/Bayesian information criterion.

A more detailed and formal statistical analytic plan (SAP) will be developed and finalized during the study. The SAP will include detailed descriptions for evaluating our study outcomes including BHPro, cognition, physical activity and sleep, and recruitment metrics.

13.2.1 Sex and Gender Analysis

Sex-stratification will be used in analyses as appropriate. Where appropriate and available, sex-specific normative data will be used in the scoring of cognitive tests. In assessing the psychometric properties of composites, the cohort will be divided into groups based on sex.

14.0 RECORDING AND COLLECTION OF DATA

14.1 Case Report Form

See [Appendix 5](#) for the Flow of Data Figure.

14.1.1 Standardized Subject Demographic and Clinical-Research Meta-Data

Demographic, clinical, and remote assessment data will be entered into the LORIS system.

The Investigator and local site study personnel will be trained on case report form (CRF) and electronic case report form (eCRF) completion and data entry into the LORIS system. The investigator is responsible for all entries in the CRF/eCRF for completeness, accuracy and clarity. The investigator or designee should complete the CRF/eCRF as soon as possible after the information is collected. The investigator is responsible to endorse all the information recorded in the CRF/eCRF and will provide formal approval of the final submitted data.

14.1.2 Recordings of Remote Study Visits

The neuropsychological test battery administration at Screening, Baseline, and Month 12 conducted by video-conference technology (e.g. Zoom) will be recorded to assist with rater

scoring, to ensure standard administration and scoring, and to help inform the study on feasibility of remote administration of the study assessments. Raters will ask the participant for permission to record the testing session prior to initiating the recording. If the participant does not provide the rater permission to record, the neuropsychological test battery administration will proceed without recording. If video recordings are permitted per local site policy, files will only be kept for the minimum amount of time required (but no longer than 60 days from the date of recording) to allow for review of the files by local site research members and the study Supervising Neuropsychologist to ensure accuracy of scoring, completion of study CRFs and entry of study data into LORIS. Only the audio-recording file from the recorded sessions will be saved and securely stored within the LORIS system. Audio-recordings will be labelled by LORIS PSCID and be accessible to study research personnel only for the purposes described above. Once analyses for the study are complete, audio recordings will be permanently deleted from LORIS. A copy of the de-identified audio-recording will be saved on external hard drive (unlinked to the internet) and retained by the study site for the duration required according to local IRB/BEB policy and/or other applicable regulatory requirements for storage of study files.

14.1.3 **BHPro**

The BHPro website will be hosted on a secure server. De-identified data (linked to LORIS PSCID) will be uploaded (API and/or csv.format), processed, and included in the CTU dataset for long-term maintenance and secure storage on the LORIS servers.

14.1.4 **Online Cognitive Testing**

Results from the MyCogHealth “burst” cognitive testing will be automatically uploaded to a secure server maintained by McGill University (and hosted by LORIS) for data management. Data will be downloaded by study staff from The Institute on Aging and Lifelong Health (University of Victoria, BC) for cleaning and processing. Processed data will be uploaded again into LORIS for inclusion in the CTU dataset (See Appendix 5 [Figure 2](#). MyCogHealth Data Flow) and for long-term maintenance and secure storage. The MyCogHealth platform will use and be maintained by LORIS system administrators with interoperability with the LORIS system for secure access to CCNA investigators.

Web servers for the Cogniciti Brain Health Assessment are hosted in Azure App Service, including firewalls and secure data transfer between client and server. Results from the Cogniciti Brain Health Assessment will be uploaded (csv.format), processed, and included in the CTU dataset for long-term maintenance and secure storage on the LORIS servers.

14.1.5 **Actigraphy and EEG Recordings**

Actigraphy data will be downloaded from the Axivity devices by study staff for cleaning and processing, and then will be uploaded to LORIS servers to be included in the CTU dataset for analysis (See Appendix 5 [Figure 5](#). Actigraphy Data Flow), and long-term maintenance and secure storage.

EEG data stored on the CTU-provided iPod will be automatically uploaded to a manufacturer-supported cloud server at the end of each day's recording. Data scripts will automatically download data files from the manufacturer-supported server to a server at SRI for cleaning and processing. Processed data will be uploaded into LORIS to be included in the CTU dataset for

analysis (See Appendix 5 [Figure 6](#). EEG Data Flow), and long-term maintenance and secure storage.

14.1.6 **Genomics**

Raw data from genomic analysis and associated sample and experiment metadata will be de-identified and uploaded to the LORIS molecular database subsystem for long-term maintenance and secure storage and sharing.

14.2 Study Files and Patient Source Documents

Participant confidentiality is strictly held in trust by the participating investigators, research staff, and the sponsoring institution and their agents. This confidentiality is extended to cover testing of biological samples and genetic tests in addition to the clinical information relating to participants. Authorized representatives of the sponsoring institution may inspect all documents and records required to be maintained by the Investigator, including but not limited to, medical records (office, clinic or hospital) for the participants in this study. The participating site will permit access to such records. Any data, specimens, forms, reports, and other records that leave the site will be identified only by a participant identification number to maintain confidentiality.

ICH-GCP guidelines require independent inspection of clinical program activities. Such inspections may be performed at any time - before, during and/or after the study. The Investigator and study staff are responsible for maintaining the site regulatory file containing all study-related regulatory documentation that will be suitable for inspection at any time by CCNA and/or its designees. The Investigator understands and agrees to give access to the necessary documentation and files. These documents include Investigators' Study Files, original participant clinical source documents generated at the study site, original participant electronic documents or completed source document worksheets. The term "original" means the first recording of the data.

Participant clinical source documents may include, but are not limited to, participant hospital/clinic records, physicians' and nurses' notes, appointment books, laboratory reports, Electrocardiograms (ECGs), Magnetic Resonance Imaging (MRI) images, pathology and special assessment reports. The Investigator must assure that all original source documents are available to support monitoring activities.

The Investigator will ensure the site regulatory files are maintained, including essential documents such as the study protocol and its amendments, IRB/REB and regulatory approvals with associated correspondence, informed consents, staff curriculum vitae, correspondence, and other appropriate documents.

